75 incidence of DBF, length of stay, emesis, and need for NGT placement.
76

77 4. Briefly describe the research design. (*Use charts and flow diagrams if applicable.* “*See*
78 *protocol” is not an acceptable response.*)
79

80 a. Subjects: State inclusion and exclusion criteria.

81 • Inclusion criteria:

- 82 ○ Completed signed and dated informed consent form
- 83 ○ Willing to comply with all study procedures
- 84 ○ Male or female, 18 years of age or older
- 85 ○ Presenting for a schedule elective colorectal/abdominal surgery, either open
86 or laparoscopic

87 • Exclusion criteria:

- 88 ○ History of gastroparesis or known gastric/intestinal motility disorder
- 89 ○ History of gastric/bariatric surgery
- 90 ○ Intubated/sedated postoperatively
- 91 ○ Presence of open abdominal wounds (including abdominal wound vac)
- 92 ○ Patients who received a complex abdominal wall reconstruction
- 93 ○ Class III/IV Wound (Contaminated/Infected/Dirty)

- 94 ○ Surgery was emergent/urgent/unscheduled
95 ○ NGT placed or present at time of operation
96 ○ Presence of ileostomy/colostomy
97 ○ J-pouch reconstruction patients
98 ○ Currently pregnant patients
99 ○ Patients aged <18 years old
100
101 b. Procedures: Provide study visit details.
- 102 • This will be a randomized single-blinded study of handheld G-POCUS in which
103 our study population will be inpatients hospitalized after abdominal/colorectal
104 surgery at TJUH, Methodist Hospital, or Abington Hospital. Patients will be
105 randomized to an unblinded intervention arm or an unblinded standard of care
106 arm. On POD1, patients will be asked if they are having any GI symptoms. These
107 are defined as presence of nausea, emesis, belching, and/or hiccups. In the
108 intervention arm, clinicians will use the results of G-POCUS and
109 presence/absence of GI symptoms to inform decision making according to one of
110 two standardized algorithms (see Appendix). In the control arm, presence of GI
111 symptoms will be assessed, and once of two standardized algorithms which are
112 representative of the current standard of care for postoperative diet management.
113 Data from both groups will be used to determine if the G-POCUS studies' results
114 can predict the incidence of primary or secondary outcomes (control) or if
115 intervening on results of G-POCUS can decrease the incidence of undesirable
116 outcomes. This will be a multicenter study enrolling patients at TJUH, Methodist

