117 Hospital, and Abington Hospital.
- 118 c. Data analysis: *(Provide statistical design for primary endpoint only. Please*
119 *indicate how the study is powered and what statistical tool(s) will be applied.*
120 *Please do not cut and paste entire statistical section from the sponsor protocol.*
121 *Pilot studies do not require a statistical plan but need to outline how the results*
122 *will be used to power future studies.)*
123
- 124 • Sample size = 128 participants
125 80% power using 2-sided t test – would require 64 patients per group (128 total)
126 to show a 25% decrease in time to GI3 recovery in G-POCUS group vs standard
127 care group.
- 128 Sample size calculation was performed using a continuous variable as the primary
129 endpoint (number of days to GI-3 recovery), and assuming an alpha of 0.05 and a
130 power of 80%. Results from the pilot study were used to inform sample size
131 calculation. All patients in the pilot study took on average 1.5 days (SD 1-3 days)
132 to reach GI-3 recovery, while patients in the pilot study with empty stomachs on
133 G-POCUS on POD1, took 1 day on average (SD 1-2) to reach GI-3 recovery.
- 134 d. If the protocol involves sending tissue to a commercial entity, please certify that
135 the following criteria are met (see TJU policy #110.17, "Collection, storage, use
136 and distribution of tissue for research purposes"). Also, please provide a copy of
137 the sponsor contract/agreement or an e-mail from ORA certifying same. The PI
138 certifies that he or she (check applicable statements):

- Will have significant input into the study design and/or conduct of the study.
- Will receive experimental data and participate in data analysis.
- Has established the right to be a co-author on any publications related to this protocol.
- Certifies that Jefferson ORA is negotiating a sponsored research agreement, to be signed prior to work commencing.

5. Delineate procedures that are standard of care from those that are being performed specifically for the research. *Delete examples and add additional rows to table as appropriate. Provide the information to the best of your ability.*

Procedure	Research	Standard of Care
G-POCUS on POD1	X	
G-POCUS on POD 2-5, if criteria met	X	

6. Describe the Data and Safety Monitoring Plan (DSMP) for this protocol. See OHR Policy G 616 for guidance.

 X Study is minimal risk and does not require a DSMP. Accuracy of data will be confirmed by PI before study is locked.

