503 simplified consent form (e.g., OHR-8C) and/or the surrogate consent form (OHR-8B).
504 • No
505
- 506 12. Will the potential subject be informed of the research or be provided a copy of the consent to
507 review prior to the actual time of consent? If so, how much time in advance? How much time
508 will be available for the consent process?
509 • Patients will be provided a copy of the consent at the initial office visit. Typically,
510 patients are seen in the office 2 to 3 weeks prior to their scheduled operation. Patients
511 will be afforded time during the initial office visit to review the consent form and ask
512 questions. Patients will be informed that they can provide consent at that point or at any
513 point up until two weeks before their operation. They will be informed that if they are
514 undecided, need additional time to review the consent, need additional time to reach a
515 decision, or would like to further discuss the study with one of the investigators or the
516 study coordinator, then appropriate arrangements will be made.
517
518
- 519 13. What provisions will be made if the potential subject does not wish to proceed with the consent
520 interview at the first encounter?

- 521 • Patients will not be approached additional times after the first encounter. They will be
522 informed that they may contact the PI or co-investigators and further discuss participation
523 at any time after the initial interview if they so wish. Patients will receive the same
524 standard of care despite their decision to participate or not.
525

526 14. Is surrogate consent involved? YES _____ NO X

527
528 15. Will subjects be paid or receive any other inducements for participating? If yes, please explain.
529 *Please note that payment of subjects must be on a pro-rated basis unless there are compelling*
530 *reasons not to prorate. There cannot be a requirement to finish all visits in order for subjects*
531 *to be paid, as this is considered coercive.*

- 532 • No
533

534 16. Describe any steps taken to minimize the possibility of coercion or undue influence.

- 535 • Voluntary participation will be stressed. The ability of patients to have colorectal surgery
536 at Jefferson without participating in any research protocols and still be treated at the same
537 high level as all of our patients will be emphasized. Patients will also be aware that they
538 can stop study participation at any time they wish.
539

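### Enrolment is capped at exactly the 128 patients the power calculation needs, although patients are enrolled before surgery and some exclusions are settled only at or after it; the time of randomisation is not stated

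*Protocol*

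**What the plan says.** **Size.** Protocol Part A item 4c gives the basis as "80% power using 2-sided t test – would require 64 patients per group (128 total"), "assuming an alpha of 0.05". It states no allowance for loss and no replacement rule. Part B item 1 puts the total number of subjects at no more than 128.

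**Time of enrolment.** Part B item 2 describes enrolment and consent together, before surgery, in the outpatient clinic. Part F item 12 lets patients consent until two weeks before the operation.

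**Exclusions.** Part A item 4a lists, among others, "NGT placed or present at time of operation", "Intubated/sedated postoperatively", a contaminated or dirty (class III/IV) wound, an open abdominal wound, a complex abdominal wall reconstruction and a stoma.

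**Allocation.** Part A item 4b calls the study single-blinded but describes both arms as unblinded. It does not say when patients are randomised relative to surgery or to the check of exclusions. Part F item 6 identifies the treating surgeons as the principal investigator and co-investigators.

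**Later removals.** Part D items 2 and 6 say that a patient who asks for the ultrasound to stop is removed from the study. Under Part A item 1a only the intervention arm is scanned, first at 0600 on postoperative day 1 (POD1).

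**The concern.** The ceiling and the required number are the same, but they appear to count different people. The calculation needs 128 patients who contribute an outcome. The ceiling, read with Part B item 2, counts patients enrolled in clinic before anyone can know whether they will pass every exclusion. If so, each patient who later proves ineligible has used one of the 128 places, and the plan has no way to replace them.

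The second stake is validity. If randomisation takes place at enrolment, the perioperative exclusions become exclusions after randomisation. Some depend on clinical decisions, such as placing a tube at operation, taken where the treating surgeons are investigators and the arms are unblinded. The two arms could then lose different kinds of patients, and the analysis could not undo that.

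**Working it through.** **1. Which exclusions can be settled before surgery?**

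| Exclusion (Part A item 4a) | When it can be settled |
|---|---|
| Intubated or sedated postoperatively | After surgery only |
| Nasogastric tube placed at operation | At surgery only |
| Class III/IV wound | Final class at surgery |
| Complex wall reconstruction, open wound, stoma | Sometimes known or planned beforehand, sometimes not |

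At least three exclusions therefore cannot be finally checked when patients are enrolled in clinic. This does not depend on the two-week consent limit: consent on the day before surgery would also come too early.

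**2. Reproduce the plan's figure.** Inputs from Part A item 4c: two-sided t test, alpha 0.05, power 80%. For all pilot patients: "All patients in the pilot study took on average 1.5 days (SD 1-3 days"). For those with an empty stomach: "took 1 day on average (SD 1-2) to reach GI-3 recovery".

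- Standardised effect d = difference / SD = (1.5 − 1.0) / 1 = 0.5, using the lowest SD in the stated range.
- The t test at d = 0.5 needs 63.77 per group, rounded up to 64. This matches the protocol.

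This is not the effect the protocol names, which is "to show a 25% decrease in time to GI3 recovery in G-POCUS group vs standard" care. A 25% decrease from 1.5 days is 0.25 × 1.5 = 0.375 day. With SD 1 that gives d = 0.375, 113 per group, and about 56% power at 64 per group. It returns 64 only with SD = 0.375 / 0.5 = 0.75, which the protocol does not state. That is a separate matter. Here d = 0.5 is used because it reproduces the planned number and favours the plan.

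**3. Reserve in the planned size.** At d = 0.5, 64 per group gives 80.1% power. With 63 in one group and 64 in the other it is 79.8%; with 63 in each it is 79.5%. There is no spare patient.

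**4. Power if the ceiling stays at 128 and patients are lost after enrolment.** The loss rates L are assumptions. Remaining per group = 64 × (1 − L), rounded down. Enrolment needed to keep 128 = 128 / (1 − L), rounded up.

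| Assumed loss | Remaining per group | Power at d = 0.5 | Enrolment needed to keep 128 |
|---|---|---|---|
| 0% | 64 | 80.1% | 128 |
| 10% | 57 | 75.4% | 143 (142.2) |
| 20% | 51 | 70.6% | 160 |
| 25% | 48 | 67.9% | 171 (170.7) |

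Odd totals need one more patient for an even split.

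**5. Removals after allocation.** Only the intervention arm is scanned, so removal for stopping the ultrasound can occur only in that arm, and only after randomisation whenever that takes place. Moving randomisation to after surgery would not prevent these losses.

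**The case against.** The strongest reply is that 128 may mean patients randomised after surgery. Item 4b describes the study population as inpatients already hospitalised after their operation, several exclusions are worded in the past tense, and the arms do not differ until 0600 on POD1, so nothing requires earlier allocation. On that reading the perioperative exclusions are screen failures, cost no power and cannot bias the comparison. This reading is possible, but it is not what Part B says: that section caps the number enrolled and places enrolment in clinic before surgery. The reply shows that the protocol supports two readings with different consequences.

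Two stronger inferences are tempting, and the document supports neither.

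- A reader might infer that 128 enrolled cannot yield 64 per group. That follows only if the 128 counts preoperatively enrolled patients and at least one is lost.
- A reader might infer that surgeons will steer exclusions by arm. Nothing says that randomisation precedes surgery or that surgeons know the arm in theatre, so the bias is conditional.

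It is also fair to object that the loss rates have no basis in the protocol and that an elective population may lose few patients. That limits the size of the power loss. It does not restore a reserve.

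**Conclusion.** The point holds in conditional form. It is certain that the enrolment ceiling equals the number needed for analysis, that enrolment is described as preoperative, that at least three exclusions can be settled only at or after surgery, and that no allowance or replacement rule is given. If the 128 counts preoperatively enrolled patients, a single loss takes power just below 80%, and assumed losses of 10% and 20% take it to about 75% and 71%. These figures rest on d = 0.5 with SD 1 and on the assumed rates.

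The risk of bias rests on a further condition, randomisation before the exclusions are settled, which the protocol neither states nor rules out. The removal rule for patients who stop the ultrasound needs no such condition: it is written into the plan and can act on one arm only. The protocol should be changed on these points, at small cost.

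**What to change.** 1. In Part A item 4b, state that randomisation takes place after surgery, once all perioperative exclusions have been checked and before the 0600 POD1 exam.
2. In Part A item 4c, define 128 as the number randomised. In Part B item 1, set a higher ceiling for consented patients, so that screen failures before randomisation do not count toward the 128. At assumed failure rates of 10% to 25% the ceiling would be about 143 to 171. If the ceiling must stay at 128 consented, restate the power for the number expected to be evaluable.
3. State that every randomised patient is analysed in the assigned arm. In Part D items 2 and 6, replace removal from the study by stopping the scans, with outcome data still collected from the chart unless consent is withdrawn.

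**Cost:** an IRB amendment and some extra consent conversations with patients who are never randomised. The number randomised stays at 128, and no clinical rule changes.

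### The only test named for days to GI-3 recovery, a two-sample t test, makes no use of surgical approach or hospital; adjusting the mean comparison for both is a low-cost gain in precision

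*Protocol*

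**What the plan says.** Part A, item 4c of the protocol is where the form asks how the study is powered and which statistical tool will be used. The answer is "80% power using 2-sided t test", which "would require 64 patients per group (128 total") "to show a 25% decrease in time to GI3 recovery in G-POCUS group vs standard" care. The endpoint is described as continuous and counted in days: "Sample size calculation was performed using a continuous variable as the primary" "endpoint (number of days to GI-3 recovery), and assuming an alpha of 0.05 and a" power of 80%. No covariate or stratum is named.

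The pilot is summarised as follows: "All patients in the pilot study took on average 1.5 days (SD 1-3 days"), while patients with an empty stomach on postoperative day 1 "took 1 day on average (SD 1-2) to reach GI-3 recovery". No distribution, median or proportion recovering on day 1 is given.

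The inclusion criteria in item 4a admit both surgical approaches ("Presenting for a schedule elective colorectal/abdominal surgery, either open" or laparoscopic). Item 4b names three hospitals. Item 7 says that data from the intraoperative record will be reviewed and stored, so approach can be read from a source already in use.

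**The concern.** Open or laparoscopic surgery is a plausible driver of how fast the bowel recovers, and practice may differ between hospitals. Approach is settled before the first scan on postoperative day 1, and hospital is fixed at enrolment, so the intervention cannot alter either. A two-sample t test leaves any variation they explain in the error term, which widens the confidence interval and lowers power.

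This matters more than usual here because the trial has little precision to spare. At an SD of 1 day, the lowest value in the stated ranges, 64 per group gives only 56% power for a 25% decrease from 1.5 days.

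**Working it through.** **1. The plan's own figure.** For two means at two-sided 5% and 80% power, n per group ≈ 2(1.96 + 0.842)² / d² = 15.70 / d², where d is the difference divided by the SD.

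- 64 per group corresponds to d = 0.50 (15.70 / 0.25 = 62.8; 64 with the t distribution).
- A 25% decrease from 1.5 days is 0.375 day. It gives d = 0.50 only if the SD is 0.75, which is below every stated range.
- At SD 1, d = 0.375 and 113 per group are needed. With 64, power is 56%.
- 1.5 versus 1.0 days at SD 1 does give 64, but that is a 33% decrease.

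This mismatch is a separate fault. It is shown only to establish the starting point.

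**2. How adjustment acts.** If covariates explain a share R² of the outcome variance, the standard error shrinks by √(1 − R²), so d becomes d / √(1 − R²). With 64 per arm and d = 0.50:

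- R² = 0.10: 0.50 / √0.90 = 0.527, power 84%.
- R² = 0.20: 0.50 / √0.80 = 0.559, power 88%.
- No covariate: power 80%.

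The R² values are assumptions. The 80% starting point holds only if d really is 0.50.

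**3. Simulation with a skewed outcome.** All inputs except the arm size, the 25% target and the number of hospitals are assumptions.

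- Time = 1.5 days × exp(random normal with the given log-SD, plus or minus an approach effect), half the patients in each approach.
- Three hospitals with no effect.
- Intervention multiplies every time by 0.75.
- Times rounded up to whole days, minimum 1.
- 64 per arm, two-sided 5%.

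The log-SD is the spread within an approach. A log-SD of 0.81 corresponds to reading 1-3 as quartiles: ln 3 / 1.349 = 0.81. An effect of ±0.2 means that open and laparoscopic times differ by a factor e^0.4 = 1.5; ±0.4 means e^0.8 = 2.2. Monte Carlo error is about 1 point.

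| Log-SD | Approach effect | t test | Adjusted linear model |
|---|---|---|---|
| 0.50 | none | 82% | 82% |
| 0.50 | ±0.2 | 77% | 80% |
| 0.50 | ±0.4 | 62% | 77% |
| 0.66 | none | 58% | 58% |
| 0.66 | ±0.2 | 54% | 55% |
| 0.66 | ±0.4 | 45% | 52% |
| 0.81 | none | 38% | 38% |
| 0.81 | ±0.4 | 31% | 34% |

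Heteroscedasticity-robust (HC3) standard errors take back 1 to 2 points. Type I error stayed between about 4% and 6% for every model.

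**4. Would a rank test do better?** Take an assumed whole-day distribution with half the controls at day 1 (mean 2.16, SD 1.60), 64 per arm:

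- Proportional-odds shift, mean 2.16 to 1.62 (25% lower): t test 57%, Wilcoxon 67%.
- Benefit only among slow recoverers (day 3 becomes day 2, day 4 or later becomes day 3; mean 2.16 to 1.67, 23% lower): t test 60%, Wilcoxon 15%.

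The ordering reverses with the form of the effect.

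**The case against.** The strongest reply is that item 4c is a short form entry, that its t test appears in the sample-size statement, and that covariates are commonly settled in a statistical analysis plan, which is not shown. A t test with 64 per arm is also valid, since its type I error is close to 5% even with skewed whole-day data. Both parts stand: the protocol nowhere says that the final analysis will be unadjusted, and nothing here is a validity error. But the form asks which tool will be applied, and the t test is the only answer given. The point is an improvement to a stated choice.

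A reader might go further and infer that the t test should give way to a rank test on hour-level times, at no cost. The documents do not support that, for four reasons:

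- **Skew is suggested, not shown.** An average of 1 with limits 1-2 fits a pile-up at day 1, but the protocol labels the figures as averages and SDs and gives no distribution.
- **Whole-day recording is an inference** from the endpoint being a number of days.
- **The rank test is not uniformly better.** It loses heavily if the benefit falls on slow recoverers. That is plausible, because the stated hypothesis concerns diagnosing delayed bowel function and reducing its complications. It also no longer tests a 25% decrease in the mean.
- **Hour-level timing is not shown to be in the chart.** Item 7 lists treatment dates and diet at times of evaluation, but no clock time for flatus, stool or diet tolerance.

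The absence of a rule for patients who never reach GI-3 in hospital is detail that an analysis plan may supply, and is not part of this point.

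**Conclusion.** The point holds as an efficiency improvement. Adjusting the mean comparison for surgical approach and hospital keeps the quantity the trial was sized on and needs no extra patients.

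The gain depends on how prognostic approach is, which the protocol does not report. With a strong effect (open and laparoscopic times differing about 2.2-fold) it is about 15 points at log-SD 0.50, 7 at 0.66 and 3 at 0.81. With a moderate effect it is about 1 to 3 points before the small cost of robust standard errors. With no effect, 0 to 2 points are lost. These figures rest on assumed lognormal times, a uniform 25% shortening, equal numbers by approach and no hospital effect.

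A reader might infer that adjustment restores the claimed 80% power. It does not: the 25% effect and the stated SDs still do not give 64 per group.

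**What to change.** In item 4c:

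1. State the primary analysis as a linear model of days to GI-3 recovery on arm, adjusted for surgical approach (open or laparoscopic) and hospital, with terms fixed in advance.
2. Report the adjusted difference in means with a 95% CI, using robust or bootstrap standard errors because skew is likely.
3. Say whether approach means planned or as performed. If randomisation precedes surgery, planned approach is the cleaner choice.
4. Add a van Elteren test stratified by approach and hospital as a sensitivity analysis only.

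The cost is a few lines of wording. Approach can be taken from the intraoperative record that item 7 already covers, and hospital is known. The statistical price is at most about 2 points of power if neither factor is prognostic. The sample-size inputs need their own correction.

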- For Investigator Initiated Treatment Trials:
Will the study be overseen by the KCC Data Safety Monitoring Committee?
 X YES NO

If NO, please provide information regarding a DSMP or independent study monitor
Who is the monitor or describe the expertise of the DSM Committee:
What will be monitored:
Stopping rules:
Frequency of monitoring reports:

- For commercially sponsored research:
Is there a DSMP or DSMC? YES NO

If NO, please provide sponsor rationale and indicate how the site will receive information about study-wide adverse events or unanticipated problems involving risk to subjects or others?

- For NIH-sponsored studies:
Is this a National Clinical Trial Network (NCTN) study? YES NO

If NO, please provide information regarding a DSMP or independent study monitor
Who is the monitor or describe the expertise of the DSM Committee:
What will be monitored:
Stopping rules:
Frequency of monitoring reports:

182
183
184
185
186
187
188
189
190
191
192
193
194
195
196
197
198
199
200
201
202
203
204
205
206
207
208
209
210
211
212
213
214
215
216
217
218
219
220
221
222
223
224
225
226
227
228

If Jefferson is a subcontracted site of a multi-center NIH-sponsored trial, how often and by what mechanism will safety or other reports be received from the coordinating center?

7. Identify the sources of research material obtained from individually identifiable living human subjects in the form of specimens, records, or data.
 - All patient-related data will be obtained from Epic via chart review by investigators, as well as via patient interview at their preoperative clinic visit. Results of G-POCUS exams, patient demographics, patient medical history, data from the intraoperative record, data from the medication administration record, data from notes, and radiographic data obtained postoperatively will be reviewed in Epic by investigators and stored in Redcap. Name, Length of Stay, Dates (treatment), MRN#, ultrasound images, ultrasound measurements, diet at times of evaluation, patient reported symptoms of DBF and POI, and need for NGT placement will be collected.
8. The following steps must be taken to ensure that identifiable data remains confidential and secure. Please check each box to confirm your understanding. There are fields below to provide explanations and to describe deviations as well as additional measures.
 - a. A separate research chart must be maintained apart from the medical record/chart of the subject.

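### The only stated primary analysis is an unadjusted t test, which gives up precision from likely prognostic factors fixed before randomisation; the loss may be small, but the remedy is cheap

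*Protocol*

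**What the plan says.** The form field at Part A, item 4c asks how the study is powered and which statistical tools will be applied to the primary endpoint. The only tool in the reply is in the sample-size statement: "80% power using 2-sided t test – would require 64 patients per group (128 total". The endpoint is continuous, "endpoint (number of days to GI-3 recovery), and assuming an alpha of 0.05 and a" power of 80%, and the target is worded "to show a 25% decrease in time to GI3 recovery in G-POCUS group vs standard" care. No covariate, site term or stratification factor is named.

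The population is mixed. Item 4a admits patients "Presenting for a schedule elective colorectal/abdominal surgery, either open" or laparoscopic. Item 4b places them after "surgery at TJUH, Methodist Hospital, or Abington Hospital". Item 4b also says that patients are randomised, but neither when this happens relative to surgery nor whether the allocation is stratified.

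Item 7 lists the data to be taken from the chart and from an interview at the preoperative clinic visit, including "patient demographics, patient medical history, data from the intraoperative record". It does not expressly list the planned surgical approach.

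**The concern.** Hospital, type of operation and open versus laparoscopic approach may plausibly affect how quickly bowel function returns. A two-sample t test leaves whatever variation they explain in its error term. A model that includes them removes that share of the residual variance and also corrects the estimate for any imbalance on them between arms of 64.

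What is at stake is power and the width of the confidence interval, not validity. The margin is thin: the design is sized at 80% with no surplus. Item 3 of Part A describes the pilot as a study after colorectal surgery, whereas the trial also admits other abdominal surgery. The trial's variance could therefore exceed the pilot's, and adjusting for operation type would offset part of such an increase.

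**Working it through.** **Inputs from Part A, item 4c.** Two-sided t test, alpha 0.05, power 80%, 64 per arm. Target decrease 25%, which is 0.25 × 1.5 = 0.375 day if the control mean is the pilot's 1.5 days. Pilot mean in all patients 1.5 days, with the SD given as 1 to 3 days; pilot mean with an empty stomach 1 day, with the SD given as 1 to 2.

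**Step 1: reproduce 64 per arm.** With d = difference/SD, n per arm ≈ 2(1.960 + 0.842)²/d². At d = 0.50 this is 2 × 7.85/0.25 = 62.8, so 63; the exact t calculation gives 63.8, so 64. Power at 64 per arm is 80.1%. The stated size therefore implies d = 0.50. Two pairs give it: 0.5 day with SD 1.0, or 0.375 day with SD 0.75.

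**Step 2: effect of adjustment.** If the covariates explain a share R² of the variance, the residual SD is SD × √(1 − R²) and the effective d is 0.50/√(1 − R²). The Protocol gives no R², so the values below are assumptions.

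| Assumed R² | Power at 64 per arm | n per arm for 80% power | Equivalent gain in patients, 1/(1 − R²) − 1 |
|---|---|---|---|
| 0 | 80.1% | 64 | 0% |
| 0.05 | 82.1% | 61 | 5% |
| 0.10 | 84.1% | 58 | 11% |
| 0.20 | 88.1% | 52 | 25% |

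These figures ignore the degrees of freedom used: two for hospital, one for operation type and one for approach, so the residual degrees of freedom fall from 126 to 122.

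**Step 3: what R² might be.** For approach alone, R² = p(1 − p)Δ²/SD², where p is the share of open operations and Δ is their delay. Neither is in the Protocol. Assume p = 0.30 and Δ = 0.5 to 0.75 day, so the numerator is 0.21 × 0.25 = 0.0525 to 0.21 × 0.5625 = 0.118.

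- SD 0.75: R² = 9% to 21%. This SD is back-calculated and lies below the stated 1 to 3.
- SD 1.0: R² = 5% to 12%.
- SD 2.0: R² = 1% to 3%.

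**Step 4: chance imbalance.** On the same assumptions, the SD of the between-arm difference in the share of open operations is √(2 × 0.21/64) = 0.081. A 1-SD imbalance moves the arm difference by 0.081 × 0.5 to 0.75 = 0.04 to 0.06 day; a 2-SD imbalance, about one trial in 20, moves it by 0.08 to 0.12 day. Over repeated randomisations this is not an additional loss. With Δ = 0.5 and SD 1.0, the imbalance contributes (0.081 × 0.5)² = 0.0016 to the variance of the arm difference, whose total is 2 × 1.0²/64 = 0.031. That is 5%, the same R² as in Step 3.

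**Step 5: what adjustment cannot do.** Pairing the worded 0.375 day with SD 1.0, the low end of the stated range, requires 113 per arm, and 64 per arm gives 55.8% power. An assumed R² of 0.20 raises this to 65.3%, and 0.40 to 77.6%, still below 80%.

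**The case against.** The strongest reply is about scope. Item 4c is a short form field limited to the primary endpoint, with an instruction not to paste in a full statistical section. The t test appears inside the power sentence, and covariates are commonly left to a statistical analysis plan, which is not available here. This stands in part: a reader might infer that no adjustment is planned, and the Protocol does not establish that. But the field also asks which tools will be applied, and the t test is the only answer given, so recommending a better test addresses a stated choice.

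Second, a reader might infer that the t test is biased or invalid in a mixed population. It is not. Randomisation keeps the comparison unbiased, and chance imbalance is already in the standard error, so imbalance and lost precision should not be counted as two separate harms.

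Third, a reader might take the variation as known to be predictable and the data that would remove it as already in hand. The Protocol gives no site, approach or operation effect, and Part A, item 3 calls delayed bowel function and ileus very hard to predict. That remark concerns which patients develop a complication and is compatible with a modest R² for days to GI-3, but it does not support a large one. Item 7 refers to the intraoperative record, which shows the operation as performed; planned approach would have to be recorded.

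Finally, it can be said that the power statement is the larger problem. That is correct, and it is a separate point.

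**Conclusion.** The point holds as an inexpensive gain in efficiency, not as an error. The stated t test is valid; a model adjusted for hospital, operation type and approach would be at least as informative apart from a loss of about four degrees of freedom. At d = 0.50 the gain is about 2 points of power if R² is 0.05, 4 points if 0.10 and 8 points if 0.20, and nothing if these factors explain no variance. Every R² here is an assumption. If the SD is 1.0 or more, as item 4c states, the illustrative effect of approach alone falls in the lower part of that range.

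Confidence is good that adjustment is the better method and low on the size of the benefit. The result should not be read as a rescue of the sample size: the 25% target, the pilot means (1.5 to 1.0 day is a 33% decrease) and the stated SD do not reconcile, and over the R² range examined adjustment does not close that gap.

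**What to change.** In Part A, item 4c, replace the t test with a linear model of days to GI-3 recovery on arm, adjusted for hospital (three levels), operation type (colorectal or other abdominal) and surgical approach (open or laparoscopic). If a time-to-event analysis is chosen, stratify it by or adjust it for the same factors.

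Use only values fixed before randomisation. State when randomisation occurs: if it precedes surgery, use the planned approach; if it follows surgery, the approach as performed is a legitimate baseline value.

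In item 4b, state that the allocation list is stratified at least by hospital, and keep every stratification factor in the analysis model. Make the change before any outcome data are seen by arm.

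The cost is a sentence in each item, a stratified list, about four degrees of freedom, and one field for planned approach at the preoperative visit. No extra patients are needed. Reconcile the effect size, pilot means and SD in the power statement separately, and do not rely on adjustment to justify 128.
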